Investigational Product (Test lens): The test product will be rotationally stabilized astigmatic soft contact lenses in senofilcon A with a chromophore to filter High-Energy Visible Light (HEVL). Approved Product (Control lens): The control product will be DAILIES TOTAL1® for Astigmatism Contact Lenses (DT1fA).		
Wear Schedule: Daily wear		
Replacement Schedule: Daily disposable		
Primary Objective: The primary objective of this study is to estimate the incidence rate (percentage) of eyes with clinically significant slit-lamp findings (Grade 3 or 4) related to each study lens (Test lens and Control lens) after approximately 2-weeks of lens wear.		
Exploratory Objectives: The exploratory objectives of this study include the estimation of the mean difference between study lenses (Test lens and Control lens) with respect to distance monocular high luminance, high contrast (HLHC), logMAR visual acuity (at the 1-week follow-up visit), and CLUE comfort, vision, and handling scores (at the fitting, 1- and 2-week follow-up visits). Additional exploratory objectives of the study are to estimate the mean and standard deviation of the mean settled toric orientation of each study lens (Test lens and Control lens) following lens settling and after 1- and 2-weeks of lens wear, and to assess the toric lens orientation of each study lens, 1- and 3-minutes after lens insertion. Adverse events will also be monitored and collected.		
Primary endpoint: • Indicidence (percentage) of eyes with Grade 3 or 4 slit lamp findings related to the study lenses (Test lens and Control lens) after 2-week of lens wear. Exploratory endpoints: • Distance Monocular HLHC logMAR at 4m at the 1-week follow-up visit • Contact Lens User Experience (CLUE) comfort scores at the fitting, 1-, and 2-week follow-up visits • CLUE vision scores at the fitting, 1-, and 2-week follow-up visits • CLUE handling scores at the fitting, 1-, and 2-week follow-up visits • Lens orientation at 1 minute and 3 minutes following insertion at fitting • Mean Settled Lens Orientation at the fitting, 1-, and 2-week follow-up visits		

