2.2. Endpoints

Primary endpoint:

1. Percentage of Eyes with slit-lamp findings (Grade 3 or 4) related to study lens wear

Slit Lamp Findings (Grade 3 or higher) will be assessed for each subject eye at all study visits (scheduled and unscheduled). However, the primary endpoint will be the percentage of eyes with Grade 3 or higher SLFs related to study lens wear, after approximately 2 weeks of lens wear.

SLFs will be evaluated and classified using the FDA Grading scale rating from 0 to 4, where Grade 0 represents the absence of findings and 1 to 4 representing successively worse findings (i.e., Grade 1=trace, Grade 2= mild, Grade 3=moderate and Grade 4= severe).

Exploratory Endpoints:

1. Distance Monocular HLHC logMAR Visual Acuity

Visual acuity (VA) will be assessed monocularly at the 1-week follow-up visits under high-luminance high contrast (HLHC) conditions at a test distance of 4 meters using ETDRS Charts. The logMAR VA score is a continuous endpoint.

2. CLUE Comfort Scores

Subjective comfort will be assessed using the Contact Lens User Experience (CLUE) questionnaire. CLUE will be assessed at the fitting, 1- and 2-week follow-up visits. The CLUE comfort score is a conintuous endpoint.

CLUE is a validated patient-reported outcomes questionnaire to assess patient-experience attributes of soft, disposable contact lenses (comfort, vision, handling, and packaging) in a contact-lens wearing population in the US, ages 18-65. Derived CLUETM scores using Item Response Theory (IRT) follow a normal distribution with a population average score of 60 (SD 20), where higher scores indicate a more favorable/positive response with a range of 0-120. A 5-point increase in an average CLUETM score translates into 10% shift in the distribution of scores for population of soft contact lens wearers.⁵

- 3. CLUE Vision Scores at the fitting, 1-, and 2-week follow-up visits. The CLUE vision score is a conintuous endpoint.
- 4. CLUE Handling Scores at the fitting, 1-, and 2-week follow-up visits. The CLUE handling score is a conintuous endpoint.

CR-6553, v3.0 JJVC CONFIDENTIAL

5. Toric Lens Orientation

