1.30.	Schedule next visit	Schedule the next visit to occur in 7(±2) days (counting the day of this visit as day 0, the subject may return on day 5 through 9). Ensure the subject is instructed to wear the study lenses for at least 1 hour immediately prior to attending the next visit.			

VISIT 2

Visit 2 will occur 5 to 9 days following Visit 1. Subjects must present to this visit wearing the study lenses in both eyes, and lenses must have been worn for at least 1 hour prior to the visit.

		Visit 2: Follow-Up #	1			
Step	Procedure	Details				
2.1.	Wear time and compliance	Record the subjects wearing time and comfortable wearing time. Subjects must have worn lenses for at least 8 hours on at least 5 days between the dispensing visit and this visit, and for at least 1 hour prior to attending this visit.				
2.2.	Review medical history and concomitant medications	Record any changes to the (including adverse events medications.				
2.3.	Subject reported ocular symptoms	Record any subject repor response to a verbal oper questionnaire.				
2.4.	Follow-up PRO questionnaire	Subjects will complete a PRO questionnaire to assess their experience with the study lenses. The glare PRO questionnaire will be completed first, followed by the CLUE questionnaire, followed by the other PRO items.				
2.5.	Entrance visual acuity	Record the entrance Snel wearing the study lenses.		ch eye while		
2.6.	Distance ETDRS visual acuity	Measure monocular discontrast (HLHC) visual 4 meters. Measure each eye using below:	acuity using E	TDRS charts	at	
		Condition	HI	HC		
		Room illumination	> 40	0 lux		
		Chart luminance	120 - 20	00 cd/m ²		
		Eye	OD	os		
		Charts	HC-1	HC-2		
2.7.	Toric lens orientation	Recorded letter-by-letter results into EDC. Record the toric lens orientation for each eye to the nearest degree.				
2.8.	Lens removal	Remove and place both lenses into a lens case with saline solution. Do not discard the lenses.				

Visit 2: Follow-Up #1			
Step	Procedure	Details	
2.9.	Biomicroscopy	The FDA Slit Lamp Classification Scale will be used to grade findings. If any slit lamp finding is graded as 3 or worse, the subject must be discontinued, an adverse event will be recorded, and the subject will be monitored as per the guidelines given in section Error! Reference source not found Should the clearance of the fluorescein need to be expedited, preservative-free rewetting drops or artificial tears may be instilled.	

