4.4.	Remove habitual lenses (if worn)	If worn, the subject's habitual contact lenses will be removed. Lenses may be stored in a lens case, if required.	
4.5.	Biomicroscopy	The FDA Slit Lamp Classification Scale will be used to grade findings. If any slit lamp finding is graded as 3 or worse, the subject must be discontinued, an adverse event will be recorded and the subject will be monitored as per the guidelines given in section Error! Reference source not found.	
		Should the clearance of the fluorescein need to be expedited, preservative free rewetting drops or artificial tears may be instilled.	
4.6.	Continuance	Verify that the subject is eligible to continue in the study.	V S

Visit 4: Lens Fitting #2

The steps followed will be the same as those listed under Visit 1: Lens Fitting #1.

VISIT 5

Visit 5 will occur 5 to 9 days following Visit 4. Subjects must present to this visit wearing the study lenses in both eyes, and lenses must have been worn for at least 1 hour prior to the visit.

Visit 5: Follow-Up #3

The steps followed will be the same as those listed under Visit 2: Follow-Up #1.

VISIT 6

Visit 6 will occur 5 to 9 days following Visit 5. Subjects must present to this visit wearing the study lenses in both eyes, and lenses must have been worn for at least 1 hour prior to the visit.

Subjects should bring their own habitual spectacles or contact lenses to this visit to wear following study lens removal.

Visit 6: Follow-Up #4			
Step	Procedure	Details	
6.1.	Wear time and compliance	Record the subjects wearing time and comfortable wearing time. Subjects must have worn lenses for at least 8 hours on at least 5 days during the dispensing period, and for at least 1 hour prior to attending this visit.	
6.2.	Collect unworn lenses	Collect any unworn study lenses that were dispensed at the previous visit.	
6.3.	Review medical history and concomitant medications	Record any changes to the subject's medical history (including adverse events) or concomitant medications.	
6.4.	Subject reported ocular symptoms	Record any subject reported ocular symptoms in response to a verbal open-ended symptoms questionnaire.	
6.5.	Follow-up PRO questionnaire	Subjects will complete a PRO questionnaire to assess their experience with the study lenses.	
		The glare PRO questionnaire will be completed first, followed by the CLUE questionnaire, then the other PRO items, then the preference questionnaire.	

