14. STATISTICAL METHODS

14.1. General Considerations

Statistical Analysis will be undertaken by the sponsor or under the authority of the sponsor. A general description of the statistical methods to be implemented in this clinical trial is outlined below.

Descriptive statistics will be reported for all key variables as appropriate. Continuous data will be summarized descriptively by sample size (n), mean, standard deviation (SD), median, minimum (Min) and maximum (Max). Categorical data will be summarized descriptively by frequency count (n) and percentage (%) of subjects or eyes within each category level. Summary tables will be presented by event (Baseline, Fitting, 1-week follow-up, 2-week follow-up, Unscheduled and Final Evaluations) and study lens type (Test and Control) as applicable, for the analysis set of interest. The denominator for all percentages will be the number of subjects (or eyes as applicable) with available data in the lens group under consideration. Unscheduled visits and tele-visits will be summarized separately and will be excluded from the primary and secondary analysis.

All available data collected at scheduled visits will be used in the statistical summaries and analyses, with no imputation of missing data. Unscheduled visits will be summarized separately and will be excluded from the statistical analysis. All data summaries and statistical analyses will be performed using the SAS software Version 9.4 or higher (SAS Institute, Cary, NC).

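### The primary percentage counts Grade 3+ slit-lamp findings only at about 2 weeks, so a lens-related week-1 finding, which forces exit, drops out of it, as do some unscheduled-visit findings

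*Combined protocol and SAP*

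**What the plan says.** Section 2.1 sets one primary objective: the incidence, by eye and by lens, of lens-related Grade 3 or 4 slit-lamp findings after roughly two weeks of wear. Section 2.2 has findings graded at every visit, scheduled or not. A sentence opening with *However* then narrows this: "primary endpoint will be the percentage of eyes with Grade 3 or higher SLFs related to study lens wear, after approximately 2 weeks". The synopsis agrees, giving "slit lamp findings related to the study lenses (Test lens and Control lens) after 2-week of lens wear".

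Section 7.2, Visit 2, step 2.9 (1-week visit): "If any slit lamp finding is graded as 3 or worse, the subject must be discontinued". For Visit 5, the 1-week visit of the second period: "The steps followed will be the same as those listed under Visit 2: Follow-Up #1".

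Section 14.1 sets the data rules:
- "The denominator for all percentages will be the number of subjects (or eyes as applicable) with available data in the lens group under consideration".
- "All available data collected at scheduled visits will be used in the statistical summaries and analyses, with no imputation of missing data". Section 14.9 repeats that nothing is imputed.
- "Unscheduled visits and tele-visits will be summarized separately and will be excluded from the primary and secondary analysis".
- "Summary tables will be presented by event (Baseline, Fitting, 1-week follow-up, 2-week follow-up, Unscheduled and Final Evaluations", and by lens type.

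Section 14.5 tabulates the grade distribution by lens in the Safety Population. It names no visit and gives no worst-grade or cumulative rule.

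**The concern.** An incidence over a wear period should count everyone who had the event in that period. Here the event itself ends participation before the visit at which the endpoint is read. The subject with the early finding then leaves numerator and denominator together, so the loss depends on the outcome and generally lowers the percentage. Discontinued subjects may also be replaced (sections 4.3 and 8.2). A full 120 eyes could therefore complete and show 0%, with nothing in the primary figure to indicate that an event had occurred.

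This is an estimation study with no hypothesis test, so the percentage is itself the primary result. Table 7 considers only 0, 1 or 2 events, so a single event matters.

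**Working it through.** **Inputs.** 60 completers, 120 eyes, and scenarios of 0, 1 and 2 events (section 14.2, Table 7); the exit rule (step 2.9, applied again at Visit 5); the denominator and missing-data rules (sections 14.1 and 14.9). The documents give no expected number of early events, so the cases below are illustrations.

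**Table 7 first.** The exact one-sided 95% upper limit for x events in n eyes is the 0.95 quantile of Beta(x+1, n−x). With n = 120 it gives 0.02466, 0.03892 and 0.05153 for x = 0, 1, 2. Table 7 prints 0.02466, 0.03887 and 0.05158, which agrees within rounding of the proportions. The same method is used below for scale only, because section 14.5 plans no interval. It treats the two eyes of a subject as independent.

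**Which visits count.** Three places point to the 2-week visit alone: the contrast in 2.2, the synopsis wording, and the separate 1-week, 2-week, Unscheduled and Final Evaluation tables. Section 2.2 uses *However* in the same way for toric orientation, to pick the endpoint's time points out of a longer list of measurements. No section carries a week-1 or unscheduled-visit finding forward.

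**Formula.** Let N eyes be examined on a lens and E be affected in total. Let e of these be found at week 1, in k subjects who all exit. The plan reports (E − e)/(N − 2k); the incidence is E/N. The plan's figure is lower exactly when E/N < e/(2k). That means E/N below 50% if each early case has one affected eye, and below 100% if both eyes are affected.

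**Cases,** with one affected eye per affected subject. Base A: 60 subjects are examined on the lens, including the early exits (N = 120). Base B: 60 others complete and the early exits are additional (N = 120 + 2k).

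| Affected eyes (week 1 / later) | A: plan vs incidence | B: plan vs incidence |
|---|---|---|
| 1 / 0 | 0/118 = 0% vs 1/120 = 0.83% | 0/120 = 0% vs 1/122 = 0.82% |
| 0 / 2 | 2/120 = 1.67% vs the same | 2/120 = 1.67% vs the same |
| 1 / 1 | 1/118 = 0.85% vs 2/120 = 1.67% | 1/120 = 0.83% vs 2/122 = 1.64% |
| 2 / 0 | 0/116 = 0% vs 2/120 = 1.67% | 0/120 = 0% vs 2/124 = 1.61% |

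Each lost eye costs about 0.8 percentage points. One-sided 95% upper limits:
- One week-1 eye: A 2.51% vs 3.89%; B 2.47% vs 3.83%.
- Two week-1 eyes: A 2.55% vs 5.15%; B 2.47% vs 4.99%.

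As a further illustration, suppose a constant weekly risk q per eye of 0.5% to 2% (assumed). The 2-week percentage is then q against a cumulative 1 − (1 − q)². At q = 1% that is 0.0100/0.0199 = 0.50, so about half the incidence is reported.

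**Unscheduled visits.** A finding there is lost only if the subject exits, or if the grade falls below 3 by the 2-week visit. If it is still Grade 3 or higher at that visit, it counts. Step U.6 has no discontinuation rule, and section 13.3 leaves continuation after an adverse event to the investigator's judgement. For corneal findings, sections 8.2 and 13.1 make exit the more likely route. Hence some of these findings are lost, not all.

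**The case against.** The strongest reply is that section 14.5 names no visit, uses everyone given a lens, and sits under a rule that all scheduled-visit data are used. Visits 2 and 5 are scheduled, and an incidence after two weeks of wear can be read cumulatively. That reading is possible, but no section states it, and 2.2, the synopsis and the by-event tables point the other way. Even if it is what the sponsor intends, the text must say so, since two analysts could report 0% and 0.83% from the same data.

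Second, early exits receive a graded slit-lamp examination at the Final Evaluation (step F.3). It is waived when biomicroscopy has just been done at the last follow-up visit. Where it is done, it falls under a separate summary event with no route into a 2-week percentage.

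Third, little formally depends on the number: there is no test, and a week-1 finding still appears in the 1-week table and the adverse event listing. This stands, and it limits the seriousness. It does not repair the one figure that answers the primary objective.

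Fourth, the size is hypothetical. That also stands.

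Finally, a 2-week-visit percentage is a legitimate summary. It is, but it is not an incidence over the wear period when the exit rule removes cases before that visit.

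**Conclusion.** The concern holds and should be fixed. On the natural reading, the primary percentage understates incidence over the wear period whenever a lens-related Grade 3 or higher finding occurs at week 1 (given the condition on E/N above), and sometimes when one occurs at an unscheduled visit. The loss is about 0.8 percentage points per eye on a base near 120. It is zero if there are no early events, and the actual number cannot be known from the documents.

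The conclusion rests on three assumptions: the endpoint is read at Visits 3 and 6 only; step 2.9 governs at the 1-week visits despite the general discretion in section 13.3 (those two passages should be reconciled); and, for the figures, one eye is affected per affected subject.

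**What to change.** In sections 2.2, 14.1 and 14.5:

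- Define the primary event as a lens-related Grade 3 or 4 finding at any slit-lamp examination (scheduled, unscheduled or early exit) after dispensing and through the 2-week visit of that lens's period.
- Use as denominator the Safety Population eyes dispensed that lens with at least one slit-lamp examination after dispensing in that period.
- Beside the percentage, report the number of dispensed eyes with no such examination, and the number event-free but lacking a 2-week examination.
- Exempt slit-lamp findings from the unscheduled-visit exclusion in 14.1.
- Keep the 2-week-visit percentage as a supportive summary.

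The discontinuation rule is not touched. The cost is wording in three sections and two extra counts in one table, from data already collected. The reported incidence may be slightly less favourable.

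The drawback is that eyes leaving early without an event count as event-free. With one event on base B and m such subjects, the percentage is 1/(122 + 2m): 0.82% at m = 0 and 1/132 = 0.76% at m = 5. That is a much smaller distortion than reporting 0%. Findings in eyes fitted but never dispensed stay outside this definition, which suits an objective about two weeks of wear; they remain in the other safety summaries.

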2. STUDY OBJECTIVES, ENDPOINTS AND HYPOTHESES

2.1. Objectives

Primary Objective:

The primary objective of this study is to estimate the incidence rate (percentage) of eyes with clinically significant slit-lamp findings (Grade 3 or 4) related to each study lens (Test lens and Control lens) after approximately 2-weeks of lens wear.

Exploratory Objectives:

The exploratory objectives of this study include the estimation of the mean difference between study lenses (Test lens and Control lens) with respect to distance monocular high luminance, high contrast (HLHC), logMAR visual acuity (at the 1-week follow-up visit), and CLUE comfort, vision, and handling scores (at the fitting, 1- and 2-week follow-up visits). Additional exploratory objectives of the study are to estimate the mean and standard deviation of the settled toric roation of each study lens (Test lens and Control lens) following lens settling and after 1- and 2-weeks of lens wear, and to assess the toric lens orientation of each study lens, 1- and 3-minutes after lens insertion. Adverse events will also be monitored and collected.

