Toric lens orientation (scribe mark position relative to 6 o'clock) will be assessed for each eye at 1, 3 and at least 15 minutes after lens insertion at the fitting visit, and at the 1- and 2-week follow-up visits. However, toric lens orientation at 1- and 3-minutes after lens insertion at the fitting visit is the exploratory endpoint. The endpoint is the distribution (counts, percentages) of eyes for the toric Orientation (in degrees).

6. Mean Settled Lens Orientation

Lens orientation (scribe mark position relative to 6 o'clock) will be assessed for each eye at 1 minute, 3 minutes, at least 15 minutes after lens insertion; 2 additional measurements per eye following settling will also be collected. The exploratory endpoint is the lens orientation assessed at the fitting, 1-, and 2-week follow-up visits. Mean settled lens orientation is a continuous response where the mean is calculated by eye by averaging across all lens orientation measurements collected at least 15-minutes after lens insertion. The standard deviation of average settled lens orientation will also be calculated. See in Appendix D for details regarding the collection of lens orientation.

7. Adverse events (AEs) - including ocular and non-ocular. Details for AEs will be provided through listings.

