14.7. Exploratory Analyses

Summary for exploratory endpoints will be provided for both the ITT and the Per-Protocol populations. However, all analyses for exploratory endpoints will be conducted on the ITT population.

Distance Monocular HLHC logMAR visual acuity

Distance monocular HLHC logMAR visual acuity at the 1-week follow-up will be summaried and presented only descriptively by lens type accompanied with the 2-sided 95% CIs. Summary statistics are described in section 14.1.

CLUE Comfort, Vision, and Handling Scores

The analysis of exploratory endpoints of CLUE comfort, vision and handling at the fitting, 1-, and 2-week follow-up visits will be conducted separately for each CLUE domain. The exploratory analysis of each CLUE score endpoints will include the estimation of mean CLUE scores and associated 95% CIs for each study lens (Test lens and Control lens). Additionally, the mean difference between the Test and Control lens paired with the 95% CI will be calculated.

CLUE scores will be analyzed using a linear mixed model, adjusting for baseline scores as a covariate. Sequence of lens wear, study period, lens type (Test and Control), timepoint (fitting, 1-week, and 2-week follow-up visit), and the ineraction lens type by timepoint will be included as fixed effects. Other baseline characteristics such age, gender, and/or race will be included as fixed covariates when appropriate. Site and subject nested within site will be included as random effects (G-side). Residual errors from measurements within the same subject and timepoint across study period will be modeled using an unstructured covariance structure (UN). If the model does not converge, other covariance structures will be considered. The Kenward and Roger method will be used for the denominator degree of freedom. Estimates for each study lens and between study lenses (Test lens and Control lens) will be carried out using two-sided 95% CIs for the least-square mean and/or mean difference.

Toric Lens Orientation

The distribution (counts, percentages) of eyes for the toric Orientation (in degrees) at 1- and 3-minutes after lens insertion will be summarized by timepoint (fitting, 1-, and 2-week follow-up) and lens type.

Mean Settled Lens Orientation

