Mean settled lens orientation will be summarized separately for each timepoint (fitting, 1-, and 2-week follow-up visits) and lens type (Test and Control). Mean settled lens orientation is calculated by eye by averaging across all lens orientation measurements collected at least 15-minutes after lens insertion. The standard deviation of average settled lens orientation will also be calculated.

The exploratory analysis of this exploratory endpoint will include the estimation of the mean settled rotation by study lens paired with the corresponding two-sided 95% CIs for each lens, and the point estimate with the two-sided 95% CI for the mean difference.

Mean settled rotation will be analyzed using a linear mixed model. Sequence of lens wear, period, lens type, and first order carryover effect will be included in the model as fixed effects. Other baseline characteristics may be included, such as, race and age. Subject will be included as a random effect. Residual errors between measurements within a subject across periods will be modeled using an unstructured (UN) covariance structure. The Kenward and Roger Method will be used for the calculation of denominator degrees of freedom. Estimates will be calculated using two-sided 95% confidence intervals constructed for the least-square mean and/or least-square mean difference.

Adverse Events

All Adverse Events reported during this study will be provided in a listing. This listing will include subject demographic information, treatment information (associated with the time of the reported AE), AE type (ocular or non-ocular), seriousness / classification, causality or relatedness, adverse event severity, outcome, actions taken and the associated start and end date / time for each AE.

Additional exploratory analyses may be considered at the discretion of the study sponsor.

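### The settled-orientation model has no visit term and no stated fit per visit, so the visit to which its Test–Control difference refers is undefined

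*Combined protocol and SAP*

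**What the plan says.** Section 2.1 asks for orientation "following lens settling and after 1- and 2-weeks of lens wear", and section 2.2 defines the endpoint at the same three times: "The exploratory endpoint is the lens orientation assessed at the fitting, 1-, and 2-week follow-up visits". By the visit schedule these are Visits 1 and 4 (fitting), 2 and 5 (1 week), and 3 and 6 (2 weeks).

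Section 14.7 then plans two things.

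- A descriptive summary: "Mean settled lens orientation will be summarized separately for each timepoint (fitting, 1-, and 2-week follow-up visits) and lens type (Test and Control").
- A mixed-model analysis giving a mean with 95% CI for each lens and "the point estimate with the two-sided 95% CI for the mean difference". Its fixed effects are given as: "Sequence of lens wear, period, lens type, and first order carryover effect will be included in the model as fixed effects". Subject is a random effect. The residual statement is: "Residual errors between measurements within a subject across periods will be modeled using an unstructured (UN) covariance structure".

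The CLUE scores are measured at the same three times. Their model, a few paragraphs earlier, adds "timepoint (fitting, 1-week, and 2-week follow-up visit), and the ineraction lens type by timepoint will be included as fixed effects".

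**The concern.** The endpoint has three visits, but the model written for it mentions none. Nothing says whether the data from fitting, 1 week and 2 weeks go into one fit, into three fits, or whether only one visit is used. Two programmers could follow section 14.7 faithfully, and one would deliver a single Test–Control difference while the other delivered three.

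The visits are not interchangeable. At fitting, the settled readings start 15 minutes or more after insertion; at follow-up, the lenses must have been worn for at least an hour. The two extra orientation samples are scheduled at Visits 1, 3, 4 and 6 but not at Visits 2 and 5, so the 1-week value rests on one reading per eye while the others average up to three. If the lens difference changes between visits, a single averaged difference and its CI may describe none of them.

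**Working it through.** The documents give no figure for settled orientation, so there is no planned number to reproduce. The check is of the model terms, followed by an illustration of size.

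**1. The two models side by side (section 14.7)**

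| | Settled orientation | CLUE |
|---|---|---|
| Fixed effects | sequence, period, lens type, first-order carryover | baseline score, sequence, period, lens type, timepoint, lens × timepoint |
| Residual covariance | within subject, across periods | within subject and timepoint, across periods |
| Lens difference at a given visit | not obtainable from one fit to all visits | obtainable |

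**2. What one fit to all visits would estimate.** Set carryover aside (see step 4). With sequence, period and lens type, and complete data, the lens contrast weights each visit's difference by 1/3:

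pooled difference = (d_fitting + d_1wk + d_2wk) / 3

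For example, +3, +1 and −1 degrees give (3 + 1 − 1)/3 = +1.

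**3. Illustration of size.** All inputs except the 60 completers are assumptions: the SD of a subject's Test–Control difference is 5 degrees at each visit, and the correlation between visits is 0.4.

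- Variance of a subject's three-visit average: 25 × (1 + 2 × 0.4)/3 = 15.
- SE of the pooled difference: √(15/60) = 0.50 degrees. The 95% half-width is 1.96 × 0.50 = 0.98.
- True differences 4, 0, 0: the pooled mean is 4/3 = 1.33. It lies 2.67/0.50 = 5.3 SE from the fitting value and 1.33/0.50 = 2.67 SE from the other two. The normal approximation gives coverage of about 0% at fitting and Φ(1.96 − 2.67) ≈ 24% at each follow-up. A simulation of 4,000 trials gives 0.1%, 26% and 26%.
- True differences 2, 0, −2: the pooled mean is 0, and the outer visits lie 2/0.50 = 4 SE away. Coverage is Φ(1.96 − 4) ≈ 2% at each (simulation: 3% and 2%) and 95% at 1 week.
- Range: with correlation 0, SE = √(25/3/60) = 0.37; with correlation 1, SE = 5/√60 = 0.65. In the 4, 0, 0 case, coverage of the follow-up differences then runs from about 5% to about 46%. The pooled value of 1.33 does not change.
- Constant difference over visits: the average equals each visit's value, and there is no bias.

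**4. Is the lens difference estimable with the terms listed?** Code sequence +1 (Test/Control) or −1 (Control/Test), and lens +1 (Test) or −1 (Control). Carryover is 0 in period 1; in period 2 it is +1 after Test and −1 after Control.

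| Sequence | Period | Lens | Carryover | (sequence − lens)/2 |
|---|---|---|---|---|
| +1 | 1 | +1 | 0 | 0 |
| +1 | 2 | −1 | +1 | +1 |
| −1 | 1 | −1 | 0 | 0 |
| −1 | 2 | +1 | −1 | −1 |

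Carryover is an exact combination of sequence and lens. Rank checks give:

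| Model | Columns | Rank | Lens difference estimable |
|---|---|---|---|
| As listed (all visits or one visit) | 5 | 4 | no |
| Carryover dropped, one fit per visit | 4 | 4 | yes, at each visit |
| Carryover dropped, timepoint and lens × timepoint added | 8 | 8 | yes, at all three visits |
| Carryover and sequence kept, both timepoint terms added | 9 | 8 | no |

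Adding visit structure alone therefore does not repair the model.

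**The case against.** The strongest reply is that pooling is nowhere stated. The subsection opens with a split by timepoint, and its residual covariance runs across periods only. A model meant to be run once per visit would look like that, with timepoint absent from both the fixed effects and the residuals. This stands: a reader might infer that the plan commits to one pooled difference, but the text neither says so nor excludes fits by visit. It does not settle the matter the other way either. Section 14.7 treats summaries (ITT and Per-Protocol) separately from analyses (ITT only), and the split by timepoint is attached to the summary. Section 14.1 sends all scheduled-visit data into the analyses.

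Second, a reader might infer that the per-visit objective goes unmet. It does not. For this endpoint section 2.1 asks to "estimate the mean and standard deviation of the settled toric roation of each study lens"; a Test–Control difference is named there for acuity and CLUE, not for orientation. The planned summaries by visit and lens meet that objective and would let a reader see means that diverge between visits. The difference with CI is promised only in section 14.7, and it is that promise which lacks a visit.

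Third, a lens that is merely slow to settle is a weak example of harm. The endpoint uses only settled readings, step 1.19 requires orientation to have stabilised, and early rotation is a separate endpoint at 1 and 3 minutes. This also stands, and it makes large differences between visits less likely. It does not say which visit the reported difference belongs to.

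**Conclusion.** The point holds as a gap in specification. The settled-orientation model does not carry the visits of its own endpoint, and the visit to which its Test–Control difference and CI refer is undefined. What is lacking is a per-visit, model-based difference with CI; per-visit estimates for each lens are planned. Under a single fit, with complete data and carryover set aside, the result is the equal-weight average of the three visit differences. As literally listed, with sequence and carryover both fixed, no lens difference is estimable on any reading.

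The degrees and coverage figures show what could happen under assumed differences, SD and correlation. They do not predict this trial, and they score a CI for an average against visit values that it does not target. The study plans no hypothesis tests and the endpoint is exploratory, so error rates are not involved and the effect is on interpretation only.

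**What to change.** In section 14.7, state that the settled-orientation model is fitted separately at fitting, 1 week and 2 weeks, and that the least-square mean for each lens, the Test–Control difference and their 95% CIs are reported for each visit. Alternatively, add timepoint and lens-by-timepoint as in the CLUE model; the residual structure would then also have to cover visits within a period.

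In the same edit, remove first-order carryover from the fixed effects. The CLUE model has no such term, and section 4.2 already relies on the washout to limit carryover.

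The cost is a few lines of text and three fits instead of one, with no new data. The CIs are somewhat wider than a pooled one: under the assumptions above, the per-visit half-width is 1.96 × 5/√60 = 1.27 degrees against 0.98, a ratio of about 1.3.
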